2.5.4 Safety Analysis

We will describe and descriptively compare proportions of those with clinical endpoints/adverse events such as hospitalizations, urgent clinic/ER visits, and death between the treatment groups, as using chi-square and Fisher's exact tests for dichotomous outcomes with such a small number of participants is unlikely to reliably demonstrate statistical significance.

2.5.5 Handling Missing Data

We will make every effort to prevent missing data by keeping the participants as engaged as possible with the study. The recommended approach for handling missing data in inferential analyses is multiple imputation⁹³⁻⁹⁵. We will construct m=5 analytic data sets after imputing each value with multiple guesses to represent inherent uncertainty in imputing missing values, analyze each data set as though complete, and finally combine the results from the analyses to obtain overall estimates. We will use SAS[®] MI and MIANALYZE procedures.

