2. We hypothesize that decreased fatigability indices will correspond to increased daily activity as measured by actigraphy.
3. We hypothesize that the primary mechanism by which NO₂ decreases fatigability is improved bioenergetics as

measured by in vivo ^{31}P MRS and in vitro mitochondrial respiration and ATP generation.

4. We hypothesize that among HFpEF patients with pulmonary hypertension, NO_2 additionally mitigates fatigability by reducing pulmonary pressures and improving right ventricular-pulmonary artery coupling.

Study Design:

This is a prospective, randomized, double blind controlled trial of oral sodium nitrite vs. placebo in adults ($n=18$), ≥ 70 years of age with HFpEF.

Subjects who meet the Inclusion Criteria and none of the Exclusion Criteria will receive oral sodium nitrite or placebo for 4 weeks. We will stratify dosing as below:

Drug:

a. oral formulation of sodium nitrite 40 mg/placebo three times daily (tid), once in the morning and again in the early afternoon and again in the evening, approximately 6 hours apart in subjects age 70 to <80 years with low risk for hypotension

b. oral formulation of sodium nitrite 20 mg/placebo three times daily (tid), once in the morning and again in the early afternoon and again in the evening, approximately 6 hours apart in subjects ≥ 80 years of age, or subjects age 70 to <80 years with risk factors for hypotension

Subjects will be evaluated as outpatients with the first dose of study drug/placebo. Blood pressure (BP), heart rate (HR), respiratory rate (RR), oxygen saturation (SpO_2), methemoglobin % (MetHb) and plasma NO_2 will be measured at baseline and during the first two hours after dosing. Frequent safety monitoring will occur during the time subjects are on drug as well as after completion of the post drug assessments, by phone and in clinic to assess adverse events (AE), interval histories, and medication compliance and to monitor NO_2 and methemoglobin levels.

Study Aims

Aim 1: To complete a randomized, placebo-controlled trial in HFpEF patients aged ≥ 70 years to assess benefits of 1 month of NO_2 vs. placebo therapy to reduce perceived and performance fatigability and to improve aerobic functional capacity.

Aim 2: To delineate factors which underlie fatigability and the utility of NO_2 to modify them.

Planned Sample Size:

18 subjects: 9 sodium nitrite and 9 placebo

- Duration of Treatment:** 4 weeks plus range 2-3 weeks for post drug outcome assessments

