2.3.4. Treatment Period

Subjects will undergo study treatment duration of 4 weeks plus up to approximately 3 weeks of sodium NO₂ or placebo three times daily. Three additional weeks are included to allow continuation of the study drug/placebo through the final outcome collection series of visits. This is considered appropriate to study benefits of oral NO₂ therapy to improve physical function in patients with HFpEF.

Randomization and Blinding

We will use the high quality pseudo-random deviate generator in SAS® (SAS Institute, Inc., Cary, North Carolina) to randomize participants to NO₂ or placebo in 1:1 ratio with a random block size. Block sizes will be revealed to the rest of the study team at the conclusion of the study to prevent educated guessing. Randomization will be stratified by the initial dose (20/40 mg) depending on whether age ≥80 or age 70-80 and hypotension risk to the extent possible within the small sample size. Study statistician will create schedules which pairwise link the randomization sequence number, participant identifier and treatment arm, and call in all prescriptions thereafter by the randomization sequence number. The independent research pharmacist at the institutional Investigational Drug Service will package all drugs/placebos to be similar in physical appearance. We have successfully employed the same process in other recently completed trials¹⁰⁵. Therefore, all participants and study personnel involved in assessments will be blind to treatment assignment.

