2.5 STATISTICAL ANALYSIS

2.5.1 Sample Size Determination

Formal sample size justifications based on statistical power for detecting significant differences at a strict 0.05 level are not applicable for a pilot study such as ours. We will use the descriptive statistics obtained herein for formal sample size and power computations in planning the larger subsequent trial to obtain more definitive findings. We will base our sample size on preliminary data from the present project, published statistical methods for sample size and power for approaches as similar as possible to the proposed analyses, and commercially available specialized software (PASS 2012[®]; Number Cruncher Statistical Systems, LLC, Kaysville, Utah) in planning the future trial to be proposed under the R01 mechanism.

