2.5.3 Efficacy Analysis

Overview-We will use SAS[®] version 9.3 (SAS Institute, Inc., Cary, North Carolina) for all analyses. The main focus of the analyses of the present pilot study will be to establish feasibility and obtain preliminary findings, and descriptive statistics needed for formal sample size and power computations for a subsequent larger randomized trial to be proposed under the R01 mechanism to obtain more definitive conclusions. Therefore, we will pay greater attention to magnitudes of effects rather than statistical significance alone, and similar to published pilot studies in other settings, also employ graphical methods such as needle plots that focus on change at the individual level rather than on average^{87, 88}. First, we evaluate the distributional characteristics of the data set, the prevalence of missing values and general data quality using appropriate descriptive statistics and graphical summarizations for all variables for each arm for each time point, as well as baseline to follow-up change scores. Second, the baseline measures and participant characteristics will be compared between the two arms using differences in magnitudes of the descriptive statistics, and independent samples *t*-, Wilcoxon rank sum, Kruskal-Wallis, chi-square or Fisher's exact tests, as appropriate. Any variables found to be meaningfully different will be noted when interpreting the findings. Third, main analyses below will be performed.

Aim 1-We will conduct Aim 1 analysis on an intention-to-treat basis. We will fit a series of linear mixed models using the SAS[®] MIXED procedure with baseline to follow-up change in primary outcome RPE, secondary outcome peak VO₂, and each of the other secondary outcomes as the

dependent variable; and treatment (NO₂/placebo), follow-up time (4 weeks) and their interaction as main factors of interest; baseline value of the dependent variable as the sole and a catch-all covariate; and a subject random effect to account for multiple follow-up measurements from each participant. We will construct appropriate means contrasts to compare the treatment groups at each of the follow-up time points. The magnitudes of the estimated means contrasts and graphical displays of individual change will be considered to support Aim 1 hypotheses rather than and in addition to statistical significance at the 0.05 level.

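### If any RPE values are missing, five imputations add avoidable Monte Carlo noise to the reported effect; inference stays valid, and a larger m removes most of the noise at almost no cost.

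*Combined protocol and SAP*

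**What the plan says.** Section 2.5.5 (Handling Missing Data) chooses multiple imputation for the inferential analyses ("The recommended approach for handling missing data in inferential analyses is multiple imputation") and sets the number of data sets: "We will construct m=5 analytic data sets after imputing each value with multiple guesses". The software is the SAS "MI and MIANALYZE procedures". Neither this section nor any other states a seed, a larger m, a rule for increasing m, or a check on Monte Carlo error.

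The analysis that this feeds is the Aim 1 model in section 2.5.3. It is intention-to-treat, with "baseline to follow-up change in primary outcome RPE" as the dependent variable and "baseline value of the dependent variable as the sole and a catch-all covariate". The planned size is "18 subjects: 9 sodium nitrite and 9 placebo" (synopsis, Planned Sample Size).

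Sections 2.5.1 and 2.5.3 put the weight on the size of the estimated effects and on plots of individual change. Significance at 0.05 is kept as a supplement, and the results are to be used in sizing a larger trial.

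**The concern.** The pooled estimate is an average over m random completions of the data. With few completions the average keeps some random error that has nothing to do with the patients and disappears as m grows. Two analysts who run the same plan on the same 18 subjects with different seeds would report different effects and p-values.

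This happens only if RPE values are missing. The plan makes that foreseeable without giving a rate:

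- Tests at Visit 5, where post-treatment RPE is collected, may be left undone if they are judged unsafe or too burdensome (section 2.2, Visit 5).
- Some withdrawals for intolerance are expected (section 6.4.7, Stopping Rule).
- A subject who cannot finish the five-minute walk is assigned to the highly fatigued category, with no numeric RPE stated for the continuous analysis (section 2.2, Visit 2, fatigability assessment).

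The main stake is the effect magnitude, since that is the figure the pilot is meant to carry forward.

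**Working it through.** The plan states no dropout rate, missing fraction or Monte Carlo error, so it has no figure of its own to reproduce.

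**Inputs.** From the documents: m = 5 (2.5.5); 18 subjects, 9 per arm (synopsis); one treatment term and one baseline covariate (2.5.3). With a single follow-up time, the model has an intercept, a treatment effect and a baseline slope, so the complete-data degrees of freedom (df) are 18 − 3 = 15. Assumed: the fraction of missing information, g, at 0%, 5%, 10%, 20% and 40%.

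**Step 1: between-seed SD.** In units of the SE that unlimited imputations would give, the between-seed SD of the pooled estimate is √(g/m), and the 95% limits are ±1.96 × √(g/m).

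| g | SD, m=5 | 95% limits, m=5 | 95% limits, m=100 |
|---|---|---|---|
| 0% | 0 | 0 | 0 |
| 5% | √(0.05/5) = 0.10 | ±0.20 | ±0.04 |
| 10% | √(0.10/5) = 0.14 | ±0.28 | ±0.06 |
| 20% | √(0.20/5) = 0.20 | ±0.39 | ±0.09 |
| 40% | √(0.40/5) = 0.28 | ±0.55 | ±0.12 |

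Measured against the slightly larger m=5 pooled SE, the SD is √[(g/m)/(1+g/m)]. The limits at 10%, 20% and 40% then become ±0.27, ±0.38 and ±0.53, which is no material change. At m=50 and g = 20%, the limits are ±0.12.

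**Step 2: what Rubin's rules already count.** The efficiency of m=5 relative to unlimited imputations is 1/(1+g/m). At g = 20% this is 1/1.04 = 96%, so the SE is √1.04 = 1.02 times as large, a cost of about 2%.

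**Step 3: effect on a p-value.** Take g = 20% and m = 5. The large-sample df are (m−1)/g² = 4/0.04 = 100. The observed-data df are (16/18) × 15 × (1−0.2) = 10.7. The small-sample (Barnard–Rubin) df are 1/(1/100 + 1/10.7) = 9.6. If the result with unlimited imputations were t = 2.0, the limits of ±0.39 place a single run between about 1.6 and 2.4, with the SE held fixed.

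| t | p on 9.6 df | p on 100 df |
|---|---|---|
| 1.6 | 0.14 | 0.11 |
| 2.0 | 0.07 | 0.048 |
| 2.4 | 0.04 | 0.018 |

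The last column is what results if MIANALYZE is not given the complete-data df. That changes the p-value at t = 2.0 from 0.07 to 0.048.

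**Step 4: check by simulation.** Assumptions: 9 against 9, residual SD 1, true effect −0.8 SD, and 1 to 5 of the 18 outcomes missing completely at random. Thirty data sets per scenario were each re-imputed with 40 seeds.

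| Missing of 18 | SD/SE, m=5 | SD/SE, m=100 | Central 95% span of estimate, m=5 | Same, m=100 |
|---|---|---|---|---|
| 1 | 12% | 3% | 0.21 SD | 0.05 SD |
| 2 | 16% | 4% | 0.29 SD | 0.06 SD |
| 3 | 21% | 5% | 0.41 SD | 0.09 SD |
| 4 | 24% | 5% | 0.51 SD | 0.11 SD |
| 5 | 26% | 6% | 0.54 SD | 0.13 SD |

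The simulation agrees with the formula: 3 of 18 missing behaves much like g = 20%.

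**The case against.** The strongest reply is that m=5 is not an error. Rubin's rules include the between-imputation variance divided by m, so intervals and tests keep their properties, and the efficiency loss is small. Sampling error with 18 subjects is much larger than the seed effect. All of that stands. What remains is that sampling error cannot be removed at this size and the seed effect can.

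A second reply is that few RPE values may be missing. RPE is collected at the first post-treatment visit; section 2.2 describes the walk as feasible in heart failure patients; subjects who refuse the second biopsy after four weeks still complete the other assessments; and pilot compliance with study drug was good (2.3.6). This also stands, which is why the range starts at zero. With no missing RPE there is no imputation and no seed effect.

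A reader might infer two stronger things. One is that the primary result is bound to depend on the seed. The documents do not support that, because the effect is conditional on missing values and no rate is given. The other is that the trial's conclusion could flip at 0.05. Section 2.5.1 says "Formal sample size justifications based on statistical power for detecting significant differences at a strict 0.05 level are not applicable for a pilot study", and section 2.5.3 uses significance only alongside magnitudes and individual plots, so no verdict hangs on crossing that line. The t = 2.0 example was also placed close to the threshold, where small shifts look largest.

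**Conclusion.** The point holds as a free improvement in precision, not as a flaw in validity. If RPE values are missing, m=5 leaves a between-seed SD of about 0.10 to 0.28 SE over 5% to 40% missing information, with 95% limits of ±0.20 to ±0.55 SE. At m=100 the limits at 20% and 40% are about ±0.09 and ±0.12 SE. At 20% with small-sample df, a t of 2.0 (p about 0.07) could be reported as anything from about 1.6 (p about 0.14) to 2.4 (p about 0.04).

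The missing-information rates are assumptions. The df rest on a three-parameter model with one follow-up time. The importance is minor and lies in the effect estimate passed to the next trial.

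**What to change.** In section 2.5.5:

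- Replace m=5 with m=100, or at least 50.
- State the PROC MI seed in the SAP before outcome data are analysed. This makes the result reproducible but does not reduce the Monte Carlo error; only the larger m does that. Tying the seed to the analysis of outcome data is clearer than tying it to unblinding, because the study statistician creates the allocation schedules (2.3.4) and a biostatistician-investigator can access the code (2.3.5).
- Specify the EDF= option in MIANALYZE with the complete-data df, which is 15 for the model described, so that p-values and intervals use small-sample df.

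The cost is a few words in the SAP and seconds of computing. No visit, assessment or sample-size change is needed.

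### Section 2.5.5 gives no degrees-of-freedom rule for pooling the imputed data sets; unless the complete-data df is supplied, pooled Aim 1 tests ignore that the model has only about 15 df.

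*Combined protocol and SAP*

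**What the plan says.** Section 2.5.5 (Handling Missing Data) makes multiple imputation the approach for inferential analyses: "We will construct m=5 analytic data sets after imputing each value with multiple guesses". The team will then "analyze each data set as though complete, and finally combine the results from the analyses to obtain overall estimates", with the SAS "MI and MIANALYZE procedures". The section names no degrees-of-freedom rule, no complete-data df and no small-sample adjustment. It also gives no expected missing-data rate.

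The planned sample in the synopsis is "18 subjects: 9 sodium nitrite and 9 placebo". Section 2.5.3 (Aim 1) models change from baseline on treatment and follow-up time, with a single time of 4 weeks, and the "baseline value of the dependent variable as the sole and a catch-all covariate". The contrasts are judged by their size and by plots of individual change, "rather than and in addition to statistical significance at the 0.05 level". Section 2.5.1 declines a power calculation.

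**The concern.** When each completed data set has few residual df, the pooled test should carry that limitation forward. The classical pooling formula does not. Its df depend only on the number of imputations and the share of variance due to missing data, so they grow without bound as that share falls.

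The result is perverse. With complete data, an Aim 1 contrast is referred to a t distribution with 15 df (critical value 2.131). Once one value is missing and imputed, the reference becomes almost normal (about 1.96). Losing a patient makes the test less cautious.

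Missing values are foreseeable. Section 2.2 lets subjects skip procedures at Visits 2 and 5, where RPE and peak VO₂ are measured. Section 6.4.7 expects some subjects not to tolerate treatment and to be withdrawn, and Aim 1 is by intention to treat. At stake are the p-values, and any intervals reported, for every Aim 1 outcome with a missing value.

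**Working it through.** The plan states no interval width or error rate, so there is no figure to reproduce. The check derives what the named procedure gives with and without a complete-data df.

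**Inputs from the documents.** N = 18, 9 per arm (synopsis); m = 5 (2.5.5); significance level 0.05 (2.5.3).

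**Derived.** With one follow-up change score per patient, the Aim 1 model reduces to intercept, arm and baseline. Complete-data df: ν_com = 18 − 3 = 15.

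**Assumed.** Two-sided testing; 1–5 of 18 follow-up values missing completely at random. MIANALYZE is taken to use an infinite complete-data df unless EDF= is given. That is a property of the software, not something the documents say.

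**Formulas.** Let λ = (1 + 1/m)B/T be the share of the total variance T that comes from the between-imputation variance B.
- Classical: ν = (m − 1)/λ² = 4/λ².
- Barnard-Rubin: ν_BR = 1/(1/ν + 1/ν_obs), with ν_obs = [(ν_com + 1)/(ν_com + 3)] · ν_com · (1 − λ) = (16/18)(15)(1 − λ).
- Narrowing = 1 − t(0.975, ν)/t(0.975, ν_BR).

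Example, λ = 0.1: ν = 4/0.01 = 400; ν_obs = 13.33 × 0.9 = 12.0; ν_BR = 1/(1/400 + 1/12.0) = 11.65; narrowing = 1 − 1.966/2.186 = 10.1%.

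| λ | classical df | Barnard-Rubin df | critical values | narrower than Barnard-Rubin |
|---|---|---|---|---|
| 0.05 | 1600 | 12.6 | 1.961 / 2.168 | 9.5% |
| 0.10 | 400 | 11.7 | 1.966 / 2.186 | 10.1% |
| 0.20 | 100 | 9.6 | 1.984 / 2.240 | 11.4% |
| 0.30 | 44 | 7.7 | 2.015 / 2.321 | 13.2% |
| 0.40 | 25 | 6.1 | 2.060 / 2.441 | 15.6% |

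With ν_com of 14 to 16, the range for λ from 0.1 to 0.3 is 9.4–14.2%.

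**Type I error by simulation.** No treatment effect, 9 versus 9, ANCOVA on baseline (correlation 0.6), proper normal-regression imputation, m = 5, 60,000 trials per row (Monte Carlo standard error 0.1 percentage point). The last column compares the classical interval with one calibrated to exactly 5% error.

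| missing of 18 | mean λ | size, classical df | size, Barnard-Rubin | narrower than Barnard-Rubin | narrower than exact |
|---|---|---|---|---|---|
| 1 | 0.078 | 6.7% | 4.6% | 9.9% | 7.6% |
| 2 | 0.150 | 6.8% | 4.5% | 10.9% | 7.9% |
| 3 | 0.215 | 6.6% | 4.2% | 12.1% | 7.3% |
| 4 | 0.278 | 6.8% | 4.3% | 13.5% | 8.3% |
| 5 | 0.338 | 6.8% | 4.2% | 15.2% | 8.8% |

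Shorter runs of 12,000 to 20,000 trials, some with baseline correlation 0.5, scatter between 6.4% and 7.1% under the classical df. In one of them the median classical df for 1/2/3/4 missing was 1005/240/104/56, against 12.3/11.1/9.7/8.3 with Barnard-Rubin.

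**Cross-check.** Using 1.96 where t(15) requires 2.131 gives a two-sided error of 6.9% and an interval 1 − 1.960/2.131 = 8.0% too short, in line with the last column.

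**More imputations do not help.** The classical df rise with m − 1. With m = 50 and two values missing (4,000 trials), the df were about 2,700 and the size 6.4%.

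**The case against.** **The plan does not choose the default.** A reader might infer that the trial has committed to the default df. It has not: 2.5.5 names the procedures and is silent on the rule, and the quoted text fits a small-sample df equally well. This stands. The point is an omission, and the error arises only if the option is left unset.

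**The larger width figure is not the error in coverage.** It is tempting to say that intervals are 10–13% too narrow. That compares them with Barnard-Rubin intervals, which are themselves conservative here (size 4.2–4.6%). If Barnard-Rubin were exact, a 10–13% shortfall would go with a size of 7.4–8.0%, not 6.7%. The shortfall that matches the simulated size is about 7–9%.

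**It is a pilot.** Section 2.5.1 says: "Formal sample size justifications based on statistical power for detecting significant differences at a strict 0.05 level are not applicable for a pilot study". Section 2.5.3 ranks effect sizes first, section 2.5 promises no confidence interval, and the pooling df leave point estimates unchanged. A reader might also infer that the short intervals would distort the next trial's sample size, but 2.5.1 bases that on descriptive statistics. All this lowers the stakes. It does not remove the point, because 2.5.3 keeps the 0.05 level in play for the Aim 1 contrasts.

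**The size rests on assumed missingness.** This is correct. The number missing, its mechanism and the imputation model are assumptions, although the simulated size hardly changes between one and five missing values.

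**A fixed df of 15 would be wrong for some outcomes.** Also correct. Invasive CPET is optional, and MRS excludes patients with incompatible devices or metal (3.3). The df must be set outcome by outcome.

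**Conclusion.** The point holds as an omission with a modest, measurable consequence. If the named procedure is run without a complete-data df and 1–4 of 18 follow-up values are missing, the nominal 5% test has a true size of about 6.6–7%. Intervals fall about 7–9% short of exact 95% coverage and are 10–13% narrower than Barnard-Rubin intervals.

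This rests on a complete-data df of 15 derived from the Aim 1 model, two-sided testing, values missing completely at random, and the stated software default. Outcomes with no missing values are unaffected. The documents support neither a claim that the sponsor has planned an incorrect method nor a claim that effect estimates would be biased by it.

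**What to change.** Add to 2.5.5: *Pooled inference uses the small-sample (Barnard-Rubin) degrees of freedom, with MIANALYZE EDF= set for each outcome to the complete-data residual df of its Aim 1 model (15 for outcomes analysed in all 18 patients with arm and baseline, 14 if initial dose is added, fewer for outcomes measured only in a subset such as iCPET or MRS).*

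For a subset of n patients analysed with arm and baseline, the value is n − 3, or n − 4 with initial dose. Here n counts everyone in that outcome's analysis set, including patients whose value is imputed.

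The cost is one sentence and one program option per outcome. The price in inference is slightly wider, mildly conservative intervals: simulated type I error is about 4–4.7%, not exactly 5%.
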